Post-licensure AEs in FluMist® recipients reported to VAERS (US Vaccine Adverse Event Reporting System) during the first 2 seasons of FluMist® use were published in 2005 (Izurieta 2005). There were no unexpected serious risks identified. Out of approximately 2.5 million recipients, 460 AE reports were received: 217 involved respiratory events (67 were influenza-like and 2 of these were serious influenza-like illness); 7 possible cases of anaphylaxis of which 5 were within 20 minutes of vaccination (giving an anaphylaxis rate of 2 per million vaccines which is similar to that of MMR); 47 other allergic; 2 Guillain Barre syndrome; 1 Bells palsy; 8 asthma exacerbation in individuals with a prior asthma history; 13 epistaxis; 33 abdominal symptoms; 67 constitutional symptoms (21 weakness/tiredness; 14 fever; 13 headache; 12 dizziness; 7 arthritis). There were no deaths associated with vaccination.

In children, the AE profile seems similar to that in adults. Two studies reported 11% more nasal congestion/rhinorrhea in 1038 vaccinated children aged 15 to 71 months, a greater use of analgesics and antipyretics after the first dose and a non-significant trend towards more fever and reduced activity levels (4% in both instances) in the vaccine groups compared to placebo recipients (Belshe 1998, Piedra 2002). These differences were only observed on the 2nd and 3rd days following vaccination, although these symptoms were also evident again on days 8 and 9. The odds ratios of developing significant symptoms compared to placebo up to 10 days after vaccination were as follows: runny nose/nasal congestion 1.61; vomiting 1.78; muscle ache 2.0; fever 1.52. Other reported symptoms did not occur at an increased rate after controlling for variables such as age and child care attendance. Again there were no associations between vaccine use and SAEs, otitis media or use of medications. There was a 21% reduction in the overall incidence of febrile illnesses during 8 months after the start of the study.

There are no published studies detailing safety in healthy adults following dual dosing with FluMist®. There are some published reports of safety following intranasal vaccination with precursors of FluMist, in which no increase in AEs were seen following the second dose, though reduced viral shedding was observed (Kietel 1993, Reeve 1980). However 2 doses of FluMist® one month apart is the licensed vaccine regimen for previously unvaccinated

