- Elderly subjects with chronic medical conditions. LAIV or placebo was given intranasally along with intramuscular IIV to 200 subjects aged 65 years or older who had a chronic medical condition (cardiovascular disease 65, pulmonary disease 11, diabetes mellitus 53) (Jackson 1999). Other than sore throat, which was significantly more frequently reported in LAIV than placebo recipients (15 versus 2%), the vaccine was safe and well-tolerated in this heterogeneous group of subjects.
- Pregnancy and lactation. There have been no detailed animal reproduction studies involving FluMist®, hence it is not known whether it can harm the fetus or affect reproduction capacity. In a single unpublished study of rats administered vaccine once or twice before gestation, during organogenesis or both, large doses of vaccine had no effect on pregnancy, parturition, lactation, embro-fetal or pre-weaning development, and no evidence of teratogenesis (Product Prescribing Information, Appendix 1a). It is not known if FluMist® is excreted in human milk. Although not specifically contraindicated the manufacturer advises against use of FluMist® in pregnant and nursing women.

IV.3.4. Secondary transmission of vaccine virus

Because FluMist® contains live, attenuated influenza viruses that must infect and replicate in cells lining the nasopharynx of the recipient to induce immunity, vaccine viruses capable of infection can be cultured afterwards from nasal secretions. A small study in healthy adults showed that 50% of subjects shed vaccine virus on Day 3 after vaccination, but none shed between Days 10 and 21 (Talbot 2005). In a RDBPC study in a day-care setting in children aged less than 3 years at least 1 vaccine strain was isolated from 80% of recipients during 21 days post-vaccination (Vesikari 2006). Transmission of at least 1 vaccine strain to non-vaccinated close contacts within the centre was calculated to be 2.4% (95%CI 0.13 to 4.6), while the probability of transmission to a child after contact with a single vaccinated child was 0.58% (95%CI 0-1.7). Duration of vaccine shedding has not been definitively established, though in the above study the mean duration was 7.6 days \pm 3.4 days.

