Post-licensure AEs in 2.5 million FluMist® recipients reported to VAERS during the first 2 seasons of FluMist® (Izurieta 2005) included 22 reports of possible secondary transmission of the vaccine virus from vaccinees to non-vaccinees. None of these events resulted in hospitalization. Ages ranged from 3 to 64 years. The interval from exposure to a vaccinated person to symptom-onset ranged from a few hours to 15 days. 59% of the events were transmission to a health care clinician who administered the vaccine, although almost half of the vaccinees had respiratory symptoms at the time of vaccination. Secondary transmission was not confirmed by laboratory tests in any of the cases. There have been no reports of secondary transmission to an immunosuppressed individual.

IV.4. Fluzone[®] Inactivated Influenza Vaccine

IV.4.1. Product Information

Fluzone[®] is a formaldehyde-inactivated vaccine made from influenza viruses propagated in embryonated chicken eggs and designed for intramuscular use. The virus is chemically disrupted using a surfactant and then further purified and suspended in buffered isotonic sodium chloride solution. It is then standardized according to USPHS requirements for the influenza season and formulated to contain 45 micrograms HA per 0.5ml dose in the same recommended ratio as for FluMist[®] (Section IV.3.1). Gelatin is used as a stabilizer. It is supplied both with a preservative (thiomersal, a mercury derivative) and also without any preservative, as a 0.5ml pre-filled syringe or vial. No antibiotics or latex are used in the manufacturing process. The dose for adults is 0.5ml.

IV.4.2. Safety and tolerability following single and dual dose administration in healthy subjects

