The study will benefit participating subjects in that they will receive a currently licensed influenza vaccine of proven efficacy. IIVs such as Fluzone have a vaccine efficacy of 70-90% in healthy adults if the vaccine strains are well matched to the circulating influenza strains (Fiore 2007). If the strains are not well matched then efficacy will be lower. In healthy adults there is a theoretical benefit of enhanced protection against vaccine strains following the second dose though (unlike children) this has not been rigorously evaluated in clinical trials.

Risks

The main risks to individual subjects are as follows:

• Phlebotomy. Discomfort and pain at venipuncture sites are possible. Subjects will be counseled to return to the clinic if local infection is suspected.

- HIV testing. A positive HIV test result may cause emotional distress. Pre- and posttest counseling will be given and referral to a specialist recommended by the US Embassy Medical Unit made if the subject wishes. Subjects may choose not to be informed of their HIV test result and in such a case will simply be told that they do not fulfill all the criteria for enrollment.
- Nasal wash. Mild nasal and/or sinus discomfort is possible during the procedure but should resolve as soon as the procedure is finished.
- Allergic reaction to FluMist® or Fluzone®. A history of prior sensitivity to any of the components of the study vaccines will have been sought at pre-study screening and those subjects excluded. From FluMist® post-licensure reports the rate of allergic reaction following single-dose administration is very low (2 per million doses). For Fluzone® the risk of allergic reaction is described in the package insert as rare and when it occurs it is presumably related to residual egg proteins or to antibiotics used in the manufacturing process. Following 2 doses of either vaccine it is possible there may be a greater chance of allergic reaction but the exact risk is unknown.
- Mild respiratory symptoms. These are known to occur more frequently in the 10 days after vaccination in FluMist® recipients (first dose only) than following placebo (approximately 15% more common). Vaccination with IIV is not associated with occurrence of respiratory symptoms.

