- Local reactions. Recipients of Fluzone® may experience soreness at the vaccination site (affects 10-64% of subjects) which can persist for 1-2 days. After a second dose of IIV one study in children aged 5-8 years found more subjects experienced soreness after the 2nd dose given 4 weeks later than after the 1st dose (71 and 55% respectively). This has not been noted in other studies of dual dosing in children or in adults with chronic medical conditions.
- Secondary transmission of FluMist® vaccine virus to a close contact (less than 1%). Because of acquired immunity to the vaccine viruses recipients of the 2-dose regimen should not be at any increased risk of secondary transmission following the 2nd dose.
- Neurological risks. There are no known neurological risks with FluMist® vaccination. With IIV vaccination neurological events have been reported rarely. The most important is Guillain-Barre syndrome (risk just over 1 additional case per 1 million vaccinated with single dose). Other rare but reported neurological events have been associated temporally with IIV, including encephalopathy, optic neuritis, partial facial paralysis and brachial plexus neuropathy. These are almost always self-limiting.

These risks will be discussed at the time of study enrollment and in the informed consent document.

XIII.3. Blood Draws

The total volume of blood drawn in this study will be approximately 243 ml over 12 weeks. This is much lower than the generally accepted maximum amount of 550 ml over a 3-month period. The maximum draw on any day will be on Days 0, 14 and 70 when 70ml will be drawn. The minimum period between blood draws is 14 days.

An additional 60ml may be requested from selected subjects after the original follow-up period has been completed, and at least 12 months after completion of the subjects' original study activities.

XIII.4. Sample Storage and Donation for Future Use

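### Section XIII.2 gives the FluMist anaphylaxis rate as its allergic-reaction rate, and contradicts Section IV on antibiotics in Fluzone and on first-dose soreness

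*Protocol*

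**What the plan says.** Section XIII.2 lists the risks of taking part and says that they will be discussed at enrolment and in the consent document.

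- **Allergy after FluMist.** Section XIII.2: "From FluMist® post-licensure reports the rate of allergic reaction following single-dose administration is very low (2 per million doses". Section IV.3.2, summarising post-licensure reports to the US reporting system, counts 7 possible anaphylaxis cases, 5 of them within 20 minutes, "giving an anaphylaxis rate of 2 per million vaccines which is similar to that of MMR". It then lists "47 other allergic; 2 Guillain Barre syndrome; 1 Bells palsy".
- **Allergy after Fluzone.** Section XIII.2 calls it rare and "presumably related to residual egg proteins or to antibiotics used in the manufacturing process". Section IV.4.1, on the same product: "No antibiotics or latex are used in the manufacturing process".
- **Soreness after two doses of inactivated vaccine, children aged 5 to 8.** Section XIII.2 gives 71% after dose 2 and 55% after dose 1. Section IV.4.2 gives 71% and 59%.

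Two further statements need their basis made clear. Section XIII.2 puts transmission of FluMist virus to a close contact below 1%, while Section IV.3.4 reports two different estimates. Section XIII.2 also says "There are no known neurological risks with FluMist® vaccination", while Section IV.3.2 lists the neurological reports quoted above.

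**The concern.** Section XIII.2 should restate in short form what Section IV documents. In the allergy item the number was carried over but its label was widened from anaphylaxis to allergic reaction. A reader of Section XIII.2 alone would take 2 per million to cover every allergic event, when the protocol's own source lists many more. The antibiotics and soreness items are plain contradictions between two parts of one document.

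What is at stake is the accuracy of the risk information given to subjects. Of the 26 planned subjects, 21 (arms 1, 3 and 4: 5 + 8 + 8) receive FluMist and 21 (arms 2, 3 and 4) receive Fluzone. A secondary effect concerns safety reporting. Section XI.2 judges whether an event is unanticipated partly by the frequency described in the protocol and/or consent form, and for allergic events the protocol now offers two frequencies.

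**Working it through.** **1. FluMist allergic reaction.** Inputs from Section IV.3.2: about 2.5 million recipients; 7 possible anaphylaxis reports, 5 of them within 20 minutes; 47 other allergic reports. Formula: reports divided by recipients in millions.

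The plan's own figure first: 5/2.5 = 2.0 per million. This matches the anaphylaxis rate in Section IV.3.2 exactly. None of the other counts gives 2:

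| Count | Reports | Per million | Ratio to 2 |
|---|---|---|---|
| Early anaphylaxis | 5 | 2.0 | 1.0 |
| All possible anaphylaxis | 7 | 2.8 | 1.4 |
| Other allergic alone | 47 | 18.8 | 9.4 |
| Early anaphylaxis + other allergic | 52 | 20.8 | 10.4 |
| All possible anaphylaxis + other allergic | 54 | 21.6 | 10.8 |

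Exact Poisson 95% limits for 54 reports are 16.2 to 28.2 per million. The figure of 2 per million is therefore not a rate of allergic reaction on any of these counts.

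**2. Antibiotics.** Section XIII.2 names manufacturing antibiotics as a presumed cause of Fluzone allergy, and Section IV.4.1 says that none are used. Section IV.3.1 lists an antibiotic, gentamicin sulphate, among the contents of FluMist. The two Fluzone statements cannot both stand.

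**3. First-dose soreness.** Section XIII.2 names no source, but the age group, the 4-week interval and the 71% after dose 2 all match the study in Section IV.4.2. The rise from dose 1 to dose 2 is 71 − 55 = 16 points in Section XIII.2 and 71 − 59 = 12 points in Section IV.4.2.

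**4. Transmission.** Section IV.3.4 gives 2.4% (95% CI 0.13 to 4.6) to unvaccinated close contacts in a day-care centre, and 0.58% (95% CI 0 to 1.7) to a child after contact with one vaccinated child. Below 1% agrees with the second and not with the first. Section XIII.2 does not say which it uses.

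**5. Neurological events.** Section IV.3.2 lists 2 Guillain-Barré reports and 1 Bell's palsy report after FluMist. For inactivated vaccine, Section XIII.2 does list rare neurological events that were associated only in time.

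**6. Figures that agree.** Injection-site soreness after Fluzone is 10 to 64% in both sections. Guillain-Barré after inactivated vaccine is about 1 additional case per million in both. The respiratory excess of about 15% lies between the 17% and 10% in Section IV.3.2.

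**The case against.** The strongest reply is that little turns on this in practice. The plan involves 26 FluMist doses (10 + 8 + 8), so even 21.6 per million implies 26 × 21.6/1,000,000 ≈ 0.0006 expected reports, and calling the risk very low remains fair. Section XIII.2 itself warns that the risk after two doses may be greater and is unknown. Listed hypersensitivities are excluded, and subjects are observed for 30 minutes after each dose. No endpoint or analysis is affected. The consent form is not in the file, so whether it repeats these figures cannot be checked. Section IV.7 already reports preliminary results, which suggests that vaccination was at least partly complete at this version. All of this stands and limits the consequence. It does not make the label right or remove the two contradictions.

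A reader might also infer more than the documents support:

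- *That Section XIII.2 mostly understates risk.* Of six numerical items, only the allergy figure clearly does. Three agree with Section IV, transmission agrees with one of two estimates, and the 55% enlarges the apparent second-dose increase.
- *That Section XIII.2 alone fixes what counts as unanticipated.* Section XI.2 refers to the whole protocol and/or the consent form, so Section IV counts too. Section XI.7 requires prompt reporting of serious events and deaths related to participation, whether expected or not. At most the reference frequency is ambiguous.
- *That the transmission figure is simply wrong.* Both estimates come from children under 3 in day care, and this trial enrols adults aged 18 to 49.
- *That Guillain-Barré rates after the two vaccines are comparable.* For FluMist there is only a crude count of reports, while for inactivated vaccine the protocol cites additional cases. These are different quantities, and three reports do not establish a known risk.

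**Conclusion.** The point holds for three items in Section XIII.2: one mislabelled rate and two contradictions of Section IV. The largest is the allergy figure. The stated 2 per million covers early anaphylaxis only, against a crude all-allergic reporting rate of about 22 per million. Depending on what is counted, that rate is 18.8 to 21.6 per million, or 9.4 to 10.8 times the stated value. This assumes one dose per recipient, no overlap between the 7 and the 47, and an approximate denominator. The reports are spontaneous and not adjudicated, so neither 2 nor 22 per million is an incidence, and the documents do not show how far reporting falls short. The soreness item also assumes that both sections describe the same study and the same symptom. The transmission and neurological statements are lesser matters of unclear basis. The errors deserve correction because they sit in the section meant to inform subjects, not because they change the trial's results.

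**What to change.** In Section XIII.2:

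1. Relabel 2 per million as the anaphylaxis rate, based on 5 cases within 20 minutes in about 2.5 million recipients. Add the reporting rate for all allergic events, about 22 per million, noting that it comes from spontaneous reports and is not an incidence.
2. Delete the antibiotics statement for Fluzone, or reconcile it with Section IV.4.1 against the product information.
3. Check 55% and 59% against the cited paediatric study and use one figure in both places.
4. State the basis of the transmission figure: 0.58% (0 to 1.7) per single contact and 2.4% (0.13 to 4.6) to close contacts, both from young children in day care.
5. Reconcile the FluMist neurological sentence with the 2 Guillain-Barré reports and 1 Bell's palsy report, saying that causality is not established.

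Carry the corrections into the consent text wherever it repeats these statements. The cost is a wording amendment and its ethics review, with no change to design, procedures or analysis.

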Appendix 1. Flow Diagram of Vaccine Combinations

Autologous Prime Boost

Heterologous Prime Boost
